Belantamab mafodotin (BLENREP™) is a first in-class anti-B-cell maturation antigen therapy approved for use in the United States (US) and European Union (EU) based on data from the pivotal Phase II DREAMM-2 study (Study 205678) (Lonial, 2020; Lonial, 2021a). DREAMM-2 is a phase II, open label, randomized, two-arm study investigating the efficacy and safety of two doses of belantamab mafodotin (3.4 mg/kg vs. 2.5 mg/kg) in participants with MM who had ≥ 3 prior lines of treatment, were refractory to a proteasome inhibitor and an immunomodulatory agent and had failed an anti-CD38 antibody (Lonial, 2020; Lonial, 2021a). DREAMM-2 results after 13-month follow-up showed an overall response rate (ORR) for the 97 patients who received the registration dose (i.e., 2.5 mg/kg) of 32% (97.5% confidence interval [CI], 21.7-43.6) with 58% of responders achieving a very good partial response (VGPR) or better, including 2 stringent complete responses (sCRs) and 5 CRs (Lonial, 2021a). Median estimated duration of response (DoR), OS, and progression-free survival (PFS) were 11.0 months (95% CI, 4.2 months to not reached), 13.7 months (95% CI, 9.9 months to not reached), and 2.8 months (95% CI, 1.6-3.6 months), respectively (Lonial, 2021a). The most frequent adverse reactions ($\geq 30\%$) reported from 95 patients in DREAMM-2 who received belantamab mafodotin 2.5 mg/kg were keratopathy (71%) and thrombocytopenia (38%). The most commonly reported serious adverse reactions were pneumonia (7%), pyrexia (7%) and infusion-related reactions (3%). Permanent discontinuation due to an adverse reaction occurred in 9% of patients who received belantamab mafodotin with 3% related to ocular adverse reactions.

In the EU, belantamab mafodotin was granted a Conditional Marketing Authorisation on 25 August 2020 for the treatment of MM in adult patients who have received at least four prior therapies and whose disease is refractory to at least one PI, one immunomodulatory agent, and an anti-CD38 mAb, and who have demonstrated disease progression on the last therapy. Because of the risk of ocular toxicity, the European Medicines Agency (EMA) required additional monitoring and additional risk minimisation measures in the

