8.2.3. EU Setting Considerations

8.3. Variables

8.3.1. Definitions

[figure not shown]
The following definitions apply to the different timings of data collection (see [Figure 2](#)):

- **Index date** is defined as the time of the first (non-missing) dose of belantamab mafodotin.
- **The baseline period** for data collection is defined as the time from the initial MM diagnosis until the index date (the first dose of belantamab mafodotin).
- **The post-index period** spans from the index date until the end of follow-up at 15 months, study discontinuation for any reason, informed consent withdrawal or death; whichever comes first.
- **The post-index treatment period** is defined as the duration of the belantamab mafodotin line of treatment (DoT). This spans from the index date until the confirmed decision date of permanent discontinuation of belantamab mafodotin treatment, the

confirmed date of a new line of treatment or the date of the end of follow-up at 15 months, study discontinuation for any reason, informed consent withdrawal or death; whichever comes first.

- **The study period** spans from the time from the initial MM diagnosis until the end of follow-up at 15 months, study discontinuation for any reason, informed consent withdrawal or death; whichever comes first.
- **Active treatment exposure periods** are defined as the time that belantamab mafodotin is considered to have a treatment effect during the post-index treatment period. This period includes all doses occurring within 70 days of the previous dose (belantamab mafodotin's half-life) from the date of the first belantamab mafodotin dose of that sequence to the date of the last dose +70 days or the date of the end of the post-index treatment period; whichever comes first.

Figure 2 Timings of Data Collection

[figure not shown]
Abbreviations: MM=multiple myeloma.

The following definitions apply to collection of treatment data:

- **Line of treatment** is defined as one or more completed cycles of a single agent, a regimen consisting of a combination of several drugs, or a planned sequential therapy of various regimens (Rajkumar, 2015).
- **A treatment cycle** is defined as the belantamab mafodotin label-approved dosing interval, which is 21 days (with a real-world scheduling grace period of +7 days).
- **Treatment discontinuation** is defined as a recorded clinician decision (with an associated decision date) to permanently discontinue belantamab mafodotin treatment.

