8.5. Study Size

Approximately 150 evaluable RRMM patients are planned for the study. The sample size is not based on statistical power consideration but on a conservative estimate for each country of interest based on country-specific MM incidence and prevalence rates, the percentage of patients expected to be eligible for belantamab mafodotin treatment, the expected belantamab mafodotin market uptake, site availability and the treatment landscape in terms of ongoing clinical trials.

The sample size 150 RRMM patients from EU sites is considered sufficient to meet the primary objective of describing RRMM patients treated with belantamab mafodotin per

routine clinical care in terms of demographics, disease status, clinical characteristics and treatment history.

To meet the planned number of 150 evaluable RRMM patients, the enrolment period may be extended if needed based on the actual uptake of belantamab mafodotin and site participation. Eligible RRMM patients from sites who received their first belantamab mafodotin dose before study enrolment will be invited for study participation if this is deemed necessary based on the enrolment rate in the EU. The number of patients who received their first belantamab mafodotin dose before study enrolment is expected to be low as belantamab mafodotin was either only recently launched or is in the process of being launched.

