8.7.2.4. Analysis of Other Secondary Objectives

In addition, the following will be described for the SP (overall and by line of treatment):

- Exposure-adjusted incidence rate with 95% CI, overall and by SOC and PT names
 - Defined as the number of patients with at least one (specific) AE during follow-up divided by the sum of person-months at risk in the study.
 - Person-months at risk is defined as the duration of follow-up for patients without AEs plus the duration of follow-up until the date of the first (specific) AE for patients with an AE.
- Exposure-adjusted event rate with 95% CI, overall and by SOC and PT names
 - Defined as the number of (specific) AESIs during follow-up divided by the sum of person-months at risk in the study.
 - Person-months at risk is defined as the duration of follow-up.
- For patients with dose reductions, interruptions/delays or discontinuation of belantamab mafodotin treatment **due to an ocular AESI** during the study period, the following will be summarized (overall and by comorbidity, ocular AESI type and ocular AESI severity as well as treatment dose and frequency):
 - Number and proportions of patients
 - Primary reasons for dose reductions, interruptions/delays or discontinuation of treatment due to any AE
 - Belantamab mafodotin treatment patterns after occurrence of an ocular AESI (i.e., order of treatment changes and timing)

- Median, 95% CIs and 25th and 75th percentiles using the Kaplan-Meier (KM) method for time to dose reductions, interruptions/delays or discontinuation
- Duration of dose reductions and interruptions/delays or discontinuations
- Belantamab mafodotin treatment adherence, i.e., the total duration of treatment in days divided by the total follow-up time in days.
- Belantamab mafodotin treatment persistence, i.e., the proportion of patients still on treatment at specified time points, including 3-, 6-, 12- and 15-months of follow-up
- Treatment response (e.g., sCR, CR, VGPR or PR):
 - Best treatment response during follow-up
 - Treatment response at specified time points, including 12- and 15-months of follow-up
 - Proportion of patients with a maintained response (PR or better) at specific time points, including 12- and 15-months of follow-up
 - ORR with 95% CIs calculated based on the exact binomial distribution (Clopper-Pearson method)
- Median, 95% CIs and 25th and 75th percentiles using the KM method for:
 - OS (overall and based on response / non-response to treatment)

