 - rwPFS (overall and based on response / non-response to treatment)
 - DoR
 - DoT
- OS rates with 95% CIs at specified time points, including 12- and 15-months of follow-up

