8.9.5. Patients Lost to Follow-up or without Follow-up Data

Because the follow-up duration will be 15 months, the proportion of discontinued patients might be significant given the severity of disease of the enrolled patient population. As standard of care visits are assumed to take place approximately every three weeks during belantamab mafodotin treatment this is expected to reduce loss to follow-up. Reasons for loss-to-follow-up will be recorded in the eCRF if available. Patients lost to follow-up will be compared with regard to baseline characteristics to patients with complete follow-up. Also, baseline characteristics will be compared between patients with and without follow-up data.

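### Persistence is defined as a plain proportion of the Safety Population still on treatment, so patients lost while on drug count as off treatment and it is understated; take it from the planned Kaplan-Meier curve

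*Protocol*

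**What the plan says.** Persistence is one of the other secondary objectives (Protocol section 7.2). Section 8.7.2.4 opens its list with "In addition, the following will be described for the SP (overall and by line of treatment" and defines persistence as "the proportion of patients still on treatment at specified time points, including 3-, 6-, 12- and 15-months of follow-up". It names no estimator or interval and gives no rule for patients who have died, withdrawn or been lost.

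Other items in the same list are more specific:
- ORR has Clopper-Pearson intervals.
- OS, rwPFS, DoR and duration of treatment (DoT) have Kaplan-Meier medians with 95% CIs and quartiles.
- OS alone also has time-point estimates: "OS rates with 95% CIs at specified time points, including 12- and 15-months of follow-up".

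Section 8.3.1 governs who is still on treatment and still followed. The post-index period, as the protocol calls it, "spans from the index date until the end of follow-up at 15 months, study discontinuation for any reason, informed consent withdrawal or death". The post-index treatment period, which is DoT, ends at permanent discontinuation, a new line, or any of those same follow-up endings. Section 8.9.5 warns that "the proportion of discontinued patients might be significant given the severity of disease of the enrolled patient population", and adds that visits about every three weeks on treatment should limit loss.

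**The concern.** A simple proportion at a fixed time is sound only if every patient's status at that time is known. Here it may not be. Under section 8.3.1 the treatment period of a patient who withdraws or is lost while still receiving drug closes on that day. In an SP proportion that patient is counted as no longer on treatment at every later time point, although treatment may have continued. The error runs in one direction, downward, and grows with time.

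A second problem is that the wording can be misapplied. The time points are given in months of follow-up, and follow-up ends at death. A programmer could take the denominator as patients still in follow-up, which would remove the dead and push the figure upward.

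The study tests no hypotheses (section 7), so its descriptive estimates are its product. The persistence figure could also disagree with the DoT Kaplan-Meier curve reported beside it, with nothing in the protocol to explain the difference.

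**Working it through.** The protocol states no expected persistence or loss rate, so there is no figure of its own to reproduce. The check compares what each reading of the definition would estimate.

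**Inputs**
- Median OS from the pivotal study at the registration dose: "13.7 months (95% CI, 9.9 months to not reached" (section 6.1).
- Median time on treatment is not given. Two assumed values: 2.8 months (the pivotal study's median PFS, section 6.1, as a stand-in) and 6 months (an alternative with no source in the protocol).
- Loss to follow-up is not given. Assumed 10% and 20% by the time point.
- Exponential times throughout (assumption).
- Planned size: "Approximately 150 evaluable RRMM patients are planned for the study" (section 8.5).

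**Formulas**
- True persistence, death counted as off treatment: P(t) = 0.5^(t / median time on treatment).
- Survival: S(t) = 0.5^(t / 13.7).
- Probability of not being lost by t, with loss independent of treatment status: G(t).
- SP denominator, lost counted as off treatment: P(t) × G(t).
- Denominator of patients alive and in follow-up: P(t) × G(t) / [S(t) × G(t)] = P(t) / S(t).
- Kaplan-Meier with loss censored: estimates P(t).

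**Step 1. SP denominator, the reading the section supports (6-month treatment median)**

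| Time | True P | 10% lost by t | 20% lost by t |
|---|---|---|---|
| 12 months | 25.0% | 25.0 × 0.9 = 22.5% | 25.0 × 0.8 = 20.0% |
| 15 months | 17.7% | 17.7 × 0.9 = 15.9% | 17.7 × 0.8 = 14.1% |

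The relative understatement equals the fraction lost. In 150 patients, 2.5 to 5 points is about 4 to 8 patients (150 × 0.025 = 3.75; 150 × 0.05 = 7.5). If loss occurs only after discontinuation, those patients are correctly counted as off treatment and the proportion equals P(t).

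**Step 2. Denominator of patients still in follow-up, the reading to rule out**

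| Time | S(t) | Factor 1/S(t) | P, median 2.8 months → reported | P, median 6 months → reported |
|---|---|---|---|---|
| 3 months | 0.859 | 1.16 | 47.6% → 55.4% | 70.7% → 82.3% |
| 6 months | 0.738 | 1.35 | 22.6% → 30.7% | 50.0% → 67.7% |
| 12 months | 0.545 | 1.84 | 5.1% → 9.4% | 25.0% → 45.9% |
| 15 months | 0.468 | 2.14 | 2.4% → 5.2% | 17.7% → 37.8% |

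G(t) cancels, so this inflation comes from dropping deaths and is the same with no loss at all. By 12 months the denominator would have shrunk from 150 to about 82 (150 × 0.545). With the 7 to 10 month median OS that section 6.1 quotes for existing options, the 12-month factor would be 3.28 to 2.30.

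**Step 3. Whether the planned Kaplan-Meier output already covers this.** Section 8.7.2.4 lists a median with CI and quartiles for DoT; section 3.9 lists the same for time to discontinuation. Neither lists values at 3, 6, 12 and 15 months. Nor does the DoT definition in section 8.3.1 say which of its endings are events and which are censoring. If every ending were coded as an event, the curve would give the same uncensored SP proportion.

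**The case against.** The strongest reply is that the text names a quantity, not an estimator. A Kaplan-Meier value at month 12 is also a proportion still on treatment, and section 8.7 leaves methodology and missing-data handling to the SAP. Censoring-adjusted values could be read off the planned curves. The loss bias may be small: three-weekly visits should limit loss on treatment, and only loss on treatment matters. Even at the assumed rates, 2.5 to 5 points lies inside the sampling error shown in the protocol's precision table (section 4): widths of 0.128 and 0.147 at proportions 0.2 and 0.3 with N=150, or about ±6 to 7 points.

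Much of this stands. The loss rates are assumptions and the bias could be near zero. But the definition is written out in full in a list that names an estimator or interval where one is wanted, and an SAP that follows it literally gives an uncensored proportion. Sampling error does not excuse a one-directional bias, which a confidence interval does not show.

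Two stronger readings are tempting, and the documents do not support them. A reader might infer that the protocol will divide by patients still in follow-up and so roughly double late persistence. The lead-in points to the SP, where the dead remain in the denominator and nothing doubles; the follow-up wording most naturally just marks the time point. A reader might also blame the doubling on loss to follow-up. Step 2 shows that it comes from excluding deaths.

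**Conclusion.** The point holds as a modest, one-directional bias in a named secondary measure, together with an ambiguity worth closing. With the SP denominator, persistence is understated by about the fraction lost while on treatment: 25% reads 22.5% to 20% at an assumed 10% to 20% loss, and is unbiased if all loss follows discontinuation. The in-follow-up reading would inflate 12- and 15-month values by 1.84 and 2.14, given exponential times and median OS of 13.7 months. It is not the natural reading, but the text does not exclude it. The treatment medians and loss rates are assumptions. No other endpoint is affected.

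**What to change.** Replace the persistence definition in section 8.7.2.4 with one along these lines: persistence is the Kaplan-Meier estimate of the probability of remaining on belantamab mafodotin at 3, 6, 12 and 15 months from the index date, with 95% CIs, in the whole SP, taken from the DoT curve. Events are permanent discontinuation, start of a new line of treatment, or death. Patients are censored at study withdrawal, loss to follow-up or 15 months.

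State the same event and censoring coding for DoT, so that the two outputs agree. Name death as an event explicitly: section 8.3.1 defines discontinuation as a recorded clinician decision, while Table 3 lists death among the reasons for it.

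The cost is a sentence or two and a few extra table rows; no new data are needed. The downside is that Kaplan-Meier assumes non-informative censoring. Patients who withdraw because they are doing badly would make the estimate too high. Reporting how many patients were censored while on treatment before each time point lets the reader judge how much this could matter.

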Continuous variables will be described (distribution) by their mean, standard deviation, median, first and third quartile (Q1 and Q3), extreme values (minimum and maximum) and the number of non-missing and missing data. Categorical variables will be described using frequency counts and percentages.

Data analysis:

The following measures will be reported:

- Exposure-adjusted incidence and event rates with 95% confidence intervals of ocular AESIs (i.e., at the patient level and the event level): overall and by SOC and PT terms (MedDRA classification).
- Median, 95% confidence intervals (CIs) and 25th and 75th percentiles using the Kaplan-Meier (KM) method for time to event outcomes (i.e., OS, rwPFS, DoR, time to discontinuation, time to first [specific] ocular AESI)
- OS rates with 95% CIs at specified time points, including 12- and 15-months of follow-up
- Overall response rate (ORR) with 95% CIs calculated based on the exact binomial distribution (Clopper-Pearson method).

Additional subgroup analyses will be conducted for primary and secondary outcomes by key patient characteristics (e.g., Eastern Cooperative Oncology Group [ECOG] performance status, age groups at the index date, MM subtype, retrospective vs prospective data, and presence or absence of ocular AESIs) when deemed applicable and feasible, as described in the Statistical Analysis Plan (SAP).

Details of interim analyses will be described in the SAP.

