- **Treatment interruption** is defined as withholding ≥ 1 belantamab mafodotin dose for any reason without a confirmed clinician decision to permanently discontinue treatment or initiate a new line of treatment. The time interval between doses will be >2 treatment cycles (+ 7-day grace periods).
- **Treatment delay** is defined as a delay (intentionally or unintentionally) in receiving belantamab mafodotin without skipping a dose. The time interval between doses will be >1 treatment cycle (+ a 7-day grace period) and <2 treatment cycles.

Figure 3 shows examples of treatment sequences that patients might undergo during the 15-month follow-up period.

Figure 3 Examples of treatment sequences during the post-index period

The following definitions apply to derived outcomes for statistical analyses:

- ORR is defined as the proportion of patients with a best response (sCR, CR, VGPR or partial response [PR]) during the study period evaluated by a responsible physician based on International Myeloma Working Group [IMWG] criteria if feasible or to local standard practice
- OS is defined as the time in months from the start of belantamab mafodotin treatment to the date of death due to any cause
- rwPFS is defined as the time in months from the start of belantamab mafodotin treatment to the date of the first documented disease progression or death, whichever occurs first
- DoR is defined as the time from the first documented evidence of PR or better until the earliest date of progressive disease (PD) or death among patients who achieved a response

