8.7.2.5. Subgroup analyses

In addition, the following key subgroup analyses are planned (as described above):

- Line of treatment
- Presence or absence of ocular AESIs
- Treatment dose and frequency
- Ophthalmic disease history
- Presence or absence of (specific) comorbidities
- Response / non-response to treatment

Additional subgroup analyses will be described in the SAP including rules for the minimum number of patients required per category and rules for merging categories including:

- ECOG performance status
- Age groups at the index date
- MM subtype
- Renal impairment
- Retrospective vs prospective data
- Dose interruptions vs continuous treatment
- Presence of extramedullary disease

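### OS and rwPFS are to be shown by response with the clock starting at first dose, so responders look better by construction

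*Protocol*

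**What the plan says.** Section 8.7.2.4 lists, among the Kaplan-Meier outputs with median, 95% CI and quartiles, "OS (overall and based on response / non-response to treatment" and "rwPFS (overall and based on response / non-response to treatment".

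Section 8.3.1 fixes the time origin of both endpoints at first dose: "OS is defined as the time in months from the start of belantamab mafodotin treatment to the date of death due to any cause", and "rwPFS is defined as the time in months from the start of belantamab mafodotin treatment". The only definition of a responder in that section is the one for ORR: "ORR is defined as the proportion of patients with a best response (sCR, CR, VGPR or partial response [PR]) during the study period". That status is acquired after the clock has started.

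Section 8.7.2.5 names response / non-response as a key subgroup. Neither 8.7 nor the limitations in 8.9 mentions a landmark, a time-dependent status or this source of bias.

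Two other groupings formed after the index date also appear in 8.7.2.5: "Presence or absence of ocular AESIs" as a key subgroup, and "Dose interruptions vs continuous treatment" among those whose description is left to the SAP.

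**The concern.** To be classed as a responder a patient must stay alive, and for rwPFS progression-free, until a response is documented. Someone who dies or progresses before then joins the non-responders whatever the drug might have achieved. Measured from first dose, the responder curve includes time in which no event could have occurred, and the non-responder curve collects the early events.

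A real survival difference by response may well exist. These curves cannot separate it from the part created by the grouping, so they overstate it by an unknown amount. Section 7 says the study is to add to the risk-benefit evidence and inform clinical practice, so side-by-side medians by response are likely to be read as showing what response is worth. Elsewhere the protocol handles timing properly: in 8.7.2.4, person-time for the incidence rate stops at the first event.

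**Working it through.** The protocol gives no figure for the by-response curves, so there is none to reproduce. The check asks how large a difference appears when there is no association at all.

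**Inputs from section 6.1** (the pivotal study at the registration dose): responders p = 32%; median OS 13.7 months; median PFS 2.8 months.

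**Assumptions, not in the protocol:** exponential event times. Time to response is independent of the event time, is exponential with mean m among potential responders, and counts only if it precedes the event and month 15. I took m = 1, 2, 3 months for OS and 0.75, 1, 1.5, 2 months for rwPFS. The share of potential responders is set so that 32% are observed to respond.

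**Formulas.** With λ = ln 2 / median, and ignoring the month-15 limit on response (which moves the 12-month figures by about 0.1 point at most):

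- responders: S_R(t) = exp(−λt) × [1 + λm(1 − exp(−t/m))]
- non-responders: S_N(t) = [exp(−λt) − p·S_R(t)] / (1 − p)

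The bracket exceeds 1 for every t > 0, so S_R lies above the overall curve and S_N below it. The direction is therefore built in.

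**OS example, m = 2, month 12.** λ = 0.6931/13.7 = 0.0506 and exp(−12λ) = 0.545. S_R = 0.545 × [1 + 0.0506 × 2 × 0.9975] = 0.600. S_N = (0.545 − 0.32 × 0.600)/0.68 = 0.519.

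**rwPFS example, m = 1.** λ = 0.6931/2.8 = 0.2476. S_R reaches 0.50 at 3.67 months: 0.403 × [1 + 0.2476 × 0.9745] = 0.500. S_N reaches 0.50 at 2.35 months: (0.5588 − 0.32 × 0.684)/0.68 = 0.500.

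A simulation of 2,000,000 patients, with the month-15 limit applied, agrees:

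| Endpoint | Mean onset (months) | Responders | Non-responders | Spurious rate ratio |
|---|---|---|---|---|
| 12-month OS | 1 | 57.2% | 53.2% | 0.88 |
| 12-month OS | 2 | 60.0% | 51.9% | 0.77 |
| 12-month OS | 3 | 62.5% | 50.8% | 0.70 |
| Median rwPFS (months) | 0.75 | 3.48 | 2.45 | 0.80 |
| Median rwPFS (months) | 1 | 3.67 | 2.35 | 0.75 |
| Median rwPFS (months) | 1.5 | 4.00 | 2.21 | 0.68 |
| Median rwPFS (months) | 2 | 4.26 | 2.13 | 0.63 |

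In terms of the statistic actually planned, median OS at m = 1 is 14.7 against 13.2 months. At m = 2 and 3 it is not reached by month 15 in responders, against 12.7 and 12.3 months in non-responders.

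**At 150 patients.** In 4,000 simulated studies per setting, the survival comparison leaned towards responders in 71%, 87% and 94% of studies for OS (m = 1, 2, 3) and in 95%, 99% and more than 99% for rwPFS (m = 1, 1.5, 2). About 50% would be expected without bias.

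**Effect of a landmark.** With patients grouped by status at 3 months among those alive, OS at month 12 is 63.4% in both groups (0.545/0.859 = 0.634). With a 2-month landmark for rwPFS, the remaining median is 2.8 months in both. Splitting person-time at response also returns a rate ratio of 1.00.

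**Patients kept at the landmark**, before losses for other reasons:

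- OS at 3 months: 0.5^(3/13.7) = 86%, about 129 of 150
- rwPFS at 2 months: 0.5^(2/2.8) = 61%, about 91 of 150
- rwPFS at 3 months: 0.5^(3/2.8) = 48%, about 71 of 150

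**The case against.** The strongest reply is that the study is descriptive. Section 7 says no formal hypotheses are tested, and the checklist in Annex 3 says no comparative analyses are planned; no log-rank test or hazard ratio is named. That stands as a limit on the harm: the result is a misleading display, not an inflated type I error. It does not make the estimates sound, because two medians printed side by side will be compared.

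A second reply is that section 8.7 leaves methodology to the SAP and that 8.7.2.4 does not spell out how responders are classified for these curves. This is partly true. But the protocol itself fixes the origin, the grouping and the Kaplan-Meier method, and its only responder definition is best response over follow-up. Response at the 12- and 15-month points, which 8.7.2.4 also lists, would be a still later classification.

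A reader might go further and infer that the protocol commits to survival curves by ocular AESI or by dose interruption, and so will report that patients with eye toxicity live longer. The text does not support that. Section 8.7.2.4 splits OS and rwPFS by response only. The link from ocular AESIs to survival runs through section 3.9, "Additional subgroup analyses will be conducted for primary and secondary outcomes by key patient characteristics", and that sentence goes on to make the subgroups conditional on applicability and feasibility and refers to the SAP. The interruption subgroup is named in 8.7.2.5 with no outcome attached and is left to the SAP. The same bias would arise if such curves were produced, but the protocol does not fix them.

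**Conclusion.** The point holds for OS and rwPFS by response. Followed as written, section 8.7.2.4 gives responders an advantage even if response has no bearing on outcome: roughly 4 to 12 percentage points in 12-month OS (57.2 − 53.2 to 62.5 − 50.8) and 1.0 to 2.1 months in median rwPFS (3.48 − 2.45 to 4.26 − 2.13). The rwPFS effect is large against a 2.8-month median.

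These sizes rest on exponential event times, independence and the assumed onset times, together with background rates from the pivotal study that may differ in routine care. The sign does not depend on the chosen onset times.

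For ocular AESI, interruption or any other grouping formed after the index date, the point is conditional: it applies only if the SAP splits OS or rwPFS that way.

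This should be fixed but is not critical. The primary objective, the key secondary analyses, ORR, DoR (which starts at response) and the overall OS and rwPFS estimates are unaffected.

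**What to change.** Amend 8.7.2.4, and carry the rule into the SAP:

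- For OS and rwPFS by response, classify patients by response status at a prespecified landmark among those still at risk (alive for OS; alive and progression-free for rwPFS), and start the Kaplan-Meier curves there. Three months is workable for OS. rwPFS needs an earlier point, such as 2 months, because a 3-month landmark keeps only about 48% of patients. Treating response as a time-dependent status is the alternative.
- Replace the first-dose curves by response. If they are kept, label them as not interpretable as an association between response and outcome.
- State in 8.7.2.5 that the same rule applies whenever OS or rwPFS is split by ocular AESI or any other status acquired after the index date.

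The cost is wording, plus the loss of pre-landmark events from these subgroup displays: about 14% of patients for OS at 3 months (100 − 86) and 39% for rwPFS at 2 months (100 − 61), under the assumptions above. A time-dependent status avoids that loss. Data collection does not change.
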